21.2. Authorship eligibility guidelines and any intended use of professional writers

Authorship of all manuscripts relating to this trial will be determined according to the International Committee of Medical Journal Editors criteria. All members of the TMG who have contributed to trial design, management, analysis and interpretation will be granted authorship of the Final Trial Report. The CI will retain lead author status on the Final Trial Report.

23. APPENDICES

Appendix 1 – Assessment of capacity to provide informed consent

For consent to be ethical and valid in law, participants must be capable of giving consent for themselves. A capable person will:

- understand the purpose and nature of the research
- understand what the research involves, its benefits (or lack of benefits), risks and burdens
- understand the alternatives to taking part
- be able to retain the information long enough to make an effective decision
- be able to make a free choice
- be capable of making this particular decision at the time it needs to be made (though their capacity may fluctuate, and they may be capable of making some decisions but not others depending on their complexity)

Where participants are capable of consenting for themselves but are particularly susceptible to coercion, it is important to explain how their interests will be protected.

Full title	Pilot randomised trial of functional imagery training (FIT) plus treatment as usual (TAU) versus TAU alone to reduce alcohol-related harm in patients with alcohol-related liver disease admitted to hospital
Short title	Mental imagery to reduce alcohol-related harm in patients with alcohol-related liver damage
Protocol Version	Version 3.1 (03 February 2022)
SAP Version	Version 1.0 (30 March 2023)
SAP Revisions	
Version 1.1 (30 March 2023)
 
Changes were made to the SAP after database lock and export of the data. Statisticians were not blinded to the allocations at this stage. The following changes were made to the SAP:
 
 • Added number and proportion of participants who reported not taking alcohol 7 days prior to the assessment day by allocation (page 11) and added Table 11b in Appendix (page 32). • Added text to explain use of mean (SD) or median (IQR) distribution of the data and sample size if N is small (Section 4.2 page 14). We also state that we only present summary statistics for those who complete all the visits if necessary • Kaplan-Meier survivor curves will be used to visualise the time of relapse to alcohol use by allocated group (Section 4.3 page 14). • Corrected MELD score formula in Appendix B (page 36) by replacing 132 with 1.32 in equation 2. • Modified Section 5.2: Analysis of pilot outcomes (page 18-19) to add: 
 ○ Number (percentage) of participants re-hospitalised ○ Number (percentage) of participants who relapsed to alcohol use

	Name	Signature	Date
Statistical Analysis Plan authored by:	Senior Trial Statistician: [name]		27/03/23
	Trial Statistician: [name]		29/03/2023
	Trial Statistician: [name]		27/03/2023
	([name], previously UoP)	N/A	

Approved by:	Chief Investigator: [name]		28/03/2023
	Independent Statistician: [name]		28-03-2023

ABBREVIATIONS

ALNs	Alcohol Liaison Nurses
ArLD	Alcohol-related liver disease
AUDIT	Alcohol Use Disorder Identification Test
CI	Confidence Interval
EQ-5D-5L	EuroQol 5 Dimension 5 Level
FIT	Functional Imagery Training
HEAP	Health Economic Analysis Plan
ITT	Intention To Treat
MELD	Model of End-stage Liver Disease
MI	Motivational Interviewing
QoL	Quality of Life
RCT	Randomised Controlled Trial
RUQ	Resource Use Questionnaire
SADQ	Severity of Alcohol Dependence Questionnaire
SAP	Statistical Analysis Plan
SD	Standard Deviation
SWEMWBS	Short Warwick-Edinburgh Mental Wellbeing Scale
TAU	Treatment as Usual
WEMWBS	Warwick-Edinburgh Mental Wellbeing Scale

1 INTRODUCTION

1.1 BACKGROUND AND RATIONALE FOR THE TRIAL

Alcohol-related liver disease (ArLD) is caused by long-term alcohol consumption, usually with physiological and psychological dependence, characterised by liver damage (fibrosis) leading to cirrhosis, which affects patients' quality of life (QoL) and survival¹. The only effective treatment to prevent progression of liver damage is reducing or ceasing alcohol consumption². In 2019/18 there were over 13,500 emergency hospital admission with a primary diagnosis of ArLD³. This is a crisis point in the ArLD patient's journey and research indicates this time point provides an opportunity for intervention where behaviour change is more likely to result.

Treatment as usual (TAU) is a brief intervention, a form of motivational interviewing (MI), conducted by a trained health professional, usually an alcohol liaison nurse, during the in-patient stay, lasting less than 20 minutes and signposting patients to community services, as recommended by NICE⁴. However, early relapse after hospital admission remains a challenge⁵. Functional Imagery Training (FIT) is a new treatment that combines the benefits of MI with evidence-based techniques of mental imagery exercises and training to further strengthen motivation, combat craving, and train self-management skills⁶.

As a trial of this new intervention has not been completed before in the target population, this pilot study will be used to gather the necessary operational and feasibility data to inform the design and implementation of a definitive randomised controlled trial (RCT) to assess the effectiveness of FIT in patients with ArLD admitted to hospital.

1.2 PURPOSE OF STATISTICAL ANALYSIS PLAN

The study protocol includes an outline of the statistical methods to be employed in the analysis of the trial data. The purpose of the Statistical Analysis Plan (SAP) is to provide full details of the planned statistical methods to be used in the primary report of the trial results. The SAP has been drafted following the SAP Guidelines⁷, CONSORT extension for Pilot and Feasibility Studies⁸ and also taking cognisance of the CONSORT extensions for reporting patient-reported outcomes⁹ and non-pharmacologic treatment interventions¹⁰. However, it is worth noting that as this is a pilot trial, formal/inferential statistical analysis and hypothesis testing of the outcome measures are not appropriate and thus will not be undertaken. There is a separate health economic analysis plan (HEAP).

2 TRIAL OBJECTIVES

2.1 PRIMARY OBJECTIVES

To conduct a randomised pilot trial of FIT and TAU versus TAU alone. This pilot study will provide high quality data:

1. To estimate rates of screening, recruitment, randomisation, retention, adherence to FIT/TAU and possible contamination
2. To allow a preliminary assessment of FIT intervention in the ArLD population.

2.2 SECONDARY OBJECTIVES

1. To estimate the resource use and costs associated with delivery of intervention, and to pilot methods for the cost-effectiveness framework in a full trial
2. To identify if there is a need to improve FIT training and delivery by Alcohol Liaison Nurses (ALNs) within the NHS and if so, methods for improvement.

3 TRIAL DESIGN

3.1 GENERAL DESIGN

Multicentre randomised controlled pilot trial of FIT+TAU (intervention group) vs TAU alone (control group).

[figure not shown]

Figure 1: Flow of participants' progression through the MIRAGE pilot trial.

TAU comprises of one brief MI-based session given in hospital by the ALN. All participants should receive TAU. Due to local hospital practices, participants may have received TAU prior to being approached about this study, prior to giving informed consent, or prior to completing the baseline measures and being randomised. The FIT intervention comprises of one session given face-to-face to participants before discharge from hospital, a second session given, if possible, face-to-face to patients in an outpatient clinic or via telephone and then a further seven sessions delivered by telephone over a period of 6 months.

All participants will be scheduled for follow-up at 28 (± 7), 90 (± 7) and 180 (± 14) days post-baseline. Figure 1 shows participants' progression through the study and time points they receive the FIT intervention (if allocated to TAU + FIT) and their follow-up assessments.

3.2 BLINDING

This trial is non-blinded to ALNs and participants, as it is not possible to conceal the active psychological FIT intervention from them. The outcome assessors (i.e. research team members conducting research visits) will be blinded to treatment allocation. The trial statistician undertaking the analyses will not be blinded to the treatment allocations. This SAP will be finalised prior to the end of the recruitment period, limiting any potential risk arising from the statistician not being blinded.

3.3 INCLUSION AND EXCLUSION CRITERIA

3.3.1 Inclusion Criteria

Patients must satisfy all of the following criteria to be enrolled in the study:

- Adult patients ≥ 18 years
- Able and willing to provide informed consent
- Clinical diagnosis of ArLD by at least one of the following methods
 - radiological appearance of fatty infiltration of the liver or cirrhosis
 - histological findings of cirrhosis or alcoholic steatohepatitis
 - signs consistent with chronic liver disease on physical examination
- High risk alcohol consumption (>50 units/week for males and >35 units/week for females) within 4 weeks prior to hospital admission
- Alcohol Use Disorder Identification Test (AUDIT) score¹¹ >15 during current hospital admission
- Diagnosis of alcohol dependence documented by clinician in medical records. This should be with reference to the ICD-10 meeting at least three of the following conditions:
 - strong desire or sense of compulsion to take alcohol
 - difficulties in controlling alcohol-consuming behaviour in terms of its onset, termination, or levels of use
 - a physiological withdrawal state when alcohol use has ceased or been reduced, as evidenced by: the characteristic withdrawal syndrome; or use of alcohol with the intention of relieving or avoiding withdrawal symptoms
 - evidence of tolerance, such that increased doses of alcohol are required in order to achieve effects originally produced by lower doses
 - progressive neglect of alternative pleasures or interests because of alcohol use, increased amount of time necessary to obtain or consume alcohol or to recover from its effects
 - persisting with alcohol use despite clear evidence of overtly harmful consequences.

3.3.2 Exclusion Criteria

Patients who meet any of the following criteria will be excluded from study participation:

- Any condition with an estimated life expectancy of less than 6 months
- Patients participating in concurrent interventional research
- Participants who have significant difficulties in adequate understanding of English such that they are unable to benefit from the trial intervention or sufficiently understand the trial documentation
- Prisoners
- Patients who do not have access to a telephone so would be unable to participate in FIT sessions.

3.4 OUTCOME MEASURES

3.4.1 Study Population

Information to describe the study population will include:

- Number of eligible participants
- Number willing/consenting participants
- Number of participants who withdraw/ are lost to follow-up
- Reasons for decline, ineligibility, withdrawal where available.

Collected baseline data will include:

- demographic information including gender, age, ethnicity, place of residence, living arrangements, marital status, age at completing full time education, employment status, and occupational status
- Liver disease data including
 - date of diagnosis,
 - stage of liver disease (e.g. fatty liver only, fibrosis, cirrhosis)
 - Model of End-stage Liver Disease (MELD) score¹²
 - Child's Pugh score¹³
 - known co-factors (e.g. Hepatitis B or C, non-alcoholic liver disease, haemochromatosis, Alpha-1 antitrypsin deficiency, autoimmune liver disease)
- Alcohol use data including:
 - AUDIT score
 - Severity of Alcohol Dependence Questionnaire (SADQ)¹⁴
- Participant characteristics including:
 - Substance misuse history including type, frequency and whether currently being used.
 - Comorbidities including type, year of diagnosis and whether this is ongoing
 - Surgical history including type, year and whether this is ongoing
 - Mental health history including type, year and whether this is ongoing
 - Medications including type, dose and frequency

3.4.2 Pilot Trial Outcome Measures

To facilitate the design and planning of a future definitive trial, we will gather the following outcome measures:

- Recruitment rate (overall and by site)
- Retention rate at 90 and 180 days (overall and by site)
- Intervention engagement – number/proportion of scheduled FIT sessions attended
- Duration of each FIT session
- Number/proportion of completed FIT sessions prior to each follow-up assessment
- Number/proportion of instances where:
 - 28 day follow-up occurred before FIT session 4
 - 90 day follow-up occurred before FIT session 7
 - 180 day follow-up occurred before FIT session 9
- Completeness of potential outcome measurements for definitive trial
- Number/proportion of instances the outcome assessor was un-blinded at each follow-up visit.

3.4.3 Participant-Reported and Clinical Outcome Measures

Outcome Measure	Baseline	28 days post-baseline	90 days post-baseline	180 days post-baseline
Alcohol use	X	X	X	X
SADQ	X	X	X	X
WEMWBS	X	X	X	X
SWEMWBS	X	X	X	X
Re-hospitalisation		X	X	X
Alcohol relapse		X	X	X
Alcohol metabolites				X
EQ-5D-5L*	X	X	X	X
Resource Use Questionnaire*	X		X	X

* please see separate HEAP

Table 1: Table detailing the timing of participant reported and other clinical outcomes

The participant-reported and clinical outcome measures listed in Table 1 will be collected in the pilot trial to help inform appropriate primary and secondary outcome measures for the definitive trial and to allow a preliminary assessment of FIT intervention in the ArLD population. The proposed primary outcome for a future definitive trial is change in self-reported alcohol use (grams of pure alcohol/week) between baseline and 180 (± 14) days post-baseline. The Timeline Follow-Back technique¹⁵ will be used to determine a participant's alcohol use during the 7 days immediately prior to: their hospital admission (baseline) and 28, 90 and 180 days post-baseline. The completeness of the Timeline Follow-Back data will also be assessed. We will report, for each visit after baseline, the number and proportion of participants who reported not taking alcohol 7 days prior to the assessment day by allocation.

Proposed secondary outcomes for a future definitive trial are the:

- *Severity of Alcohol Dependence Questionnaire (SADQ)*¹⁴ – This questionnaire consists of 20 items and covers the following areas of the dependency syndrome:
 - physical withdrawal symptoms; affective withdrawal symptoms
 - relief drinking
 - frequency of alcohol consumption
 - speed of onset of withdrawal symptoms.Each item of the questionnaire is scored between 0 (almost never) and 4 (nearly always)
- *Warwick-Edinburgh Mental Wellbeing Scale (WEMWBS)*¹⁷ – This questionnaire is a measurement of mental wellbeing, consisting of 14 items each with a score between 1 (None of the time) and 5 (all of the time)
- *Short Warwick-Edinburgh Mental Wellbeing Scale (SWEMWBS)*¹⁸ - This questionnaire is the short version of WEMWBS, consisting of 7 of the items from the full WEMWBS
- *Re-hospitalisation within 180 days post baseline* – Self-reported by participants or determined using hospital records at participating sites
- *Time to relapse* – Self-reported time to relapse to regular alcohol use, defined as ≥ 5 drinking days per week, or ≥ 5 units in a single day
- *Alcohol metabolites* – a urinary sample will be used to measure ethyl glucuronide ($\mu\text{g/L}$) and ethyl sulphate ($\mu\text{g/L}$), which provide a highly sensitive and specific objective quantitative measure of alcohol consumption within the preceding 72 hours
- *EuroQol 5 Dimension 5 Level (EQ-5D-5L)*¹⁶ – This quality of life questionnaire, commonly used in health economics, consists of five questions, where each question/item can be scored between 1 (no problems) and 5 (extreme problems). Further information is provided in the HEAP
- *Resource Use Questionnaire (RUQ)* – see the separate HEAP for details.

3.5 SAMPLE SIZE CALCULATION

One of the key objectives of this pilot study, to inform the definitive trial, is whether patients can be successfully recruited and followed-up. We estimate that across all sites, 24 potentially eligible ArLD patients are admitted per month. Our total recruitment target is 90 participants.

This recruitment target will allow estimation of the overall retention rate with a 95% confidence interval (CI) with precision of at least $\pm 11\%$. Assuming a non-differential retention rate of 75% at the 6-month follow-up (the anticipated primary endpoint for a definitive trial), indicates primary outcome data will be available from a minimum of 33 participants within each allocated group. This will enable appropriate estimation of key components, such as the variability in the proposed primary outcome, to inform the sample size calculations for the definitive trial.

4 STATISTICAL PRINCIPLES

4.1 RANDOMISATION, ALLOCATION CONCEALMENT AND STRATIFICATION

Participants will be allocated to receive TAU or TAU+FIT, in a 1:1 ratio, using random permuted blocks, stratified by recruiting site and the participant's baseline SADQ total score, dichotomised as ≤ 30 (moderate) or >30 (severe)¹⁹.

4.2 ANALYSIS POPULATIONS

Primary analysis (in the form of summary statistics such as means and standard deviations (SDs) or medians and interquartile ranges (IQR), where appropriate), will be undertaken on an Intention To Treat (ITT) basis, where participants are analysed according to their allocated group, regardless of adherence to the protocol or lack of participation or completion of FIT sessions if allocated to the intervention group. No formal (i.e. no hypothesis testing/inferential) analysis will be performed. Missing responses will be imputed according to the guidance set out in section 4.8.1. Any participants with non-imputable items/scores, will not be included in the ITT analysis for the outcome/time-point under consideration. We will present summary statistics of outcomes for participants who complete all visits in both groups. the changes between baseline and each of the 28, 90, and 180 day assessments, a participant will need to have non-missing or imputable data at both of the time points to be included in the analysis. Kaplan-Meier survivor curves will be used to characterise the time of relapse to alcohol use by group.

The safety population will include all participants who consent to participate in the study, with safety data collected from the time of recruitment until a participant completes or withdraws from the study. Any participant who does not attend at least one FIT session will be analysed as TAU and any participant who has received at least one FIT session will be analysed as TAU + FIT.

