17.4. Outline of statistical analyses

Trial science outcomes, such as recruitment and retention rates, completeness of outcome measures at each follow-up, will be presented as frequencies and percentages (with confidence intervals), overall and by allocated group where relevant. The timing and frequency of missing outcome data will be summarised. Individuals lost to follow-up will be compared to those who complete the pilot study to identify any potential bias.

Descriptive statistics of the participant-reported and clinical outcomes will be produced, as appropriate for each measure for each group at all timepoints. Changes, where appropriate, between baseline and 6-months will be summarised descriptively and presented by allocated group. Interval estimates of the potential intervention effect of FIT+TAU, relative to TAU only, will be produced, with the promise of the FIT intervention (as per section 4.1, objective 2) assessed using the confidence interval for the between-group difference in change in grams of pure alcohol consumed in previous week (proposed primary outcome for definitive trial).

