17.5. Participant population

As described above, the primary descriptive comparative analyses of the participant-reported and other clinical outcomes will be on an intention-to-treat basis, including all the outcome data obtained from all participants, with participants analysed in the group to which they were originally allocated. Safety data (SAEs and SARs) will be presented on a per-protocol basis.

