17.6. Procedure(s) to account for missing or spurious data

Reasons for being unable to collect data during an assessment will be recorded on the case report form where appropriate. Case report forms will be assessed for missing data by the CTU. As this is a pilot study, no imputation of missing data will be undertaken with the exception of instances where there are published methods for managing missing items in validated patient-reported outcomes.

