4.7.1 Imputation

Imputation will only be performed for missing questionnaire items when a small proportion of items are missing from an individual response. Where possible, validated, published guidelines will be followed. Any participant who misses a follow-up visit or the whole outcome measure/questionnaire, will not be imputed for that time-point or measurement. Any missing clinical measures, such as the Child Pugh score and MELD score, will not be imputed.

The published guidelines for imputation of the proposed outcomes are summarised below:

- *WEMWBS* – Impute missing items if no more than 3 are missing. The guidance suggests using the mean of all responses for the missing item or the mean of the non-missing items for the participant as possible imputation methods²⁴.

- SWEMWBS – The transformations set out in Table 17 are only valid when the response is complete, i.e. no missing values, therefore no imputation will be performed for this measure²⁴.

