5.3 PRELIMINARY ASSESSMENT OF FIT

As this is not a fully powered trial, it is inappropriate to perform any formal hypothesis tests comparing the allocated groups. However, to provide a preliminary assessment of whether FIT is a potentially useful treatment for patients with ArLD, we will calculate summary statistics for each of the participant-reported and clinical outcomes listed in section 0, by allocated group.

For continuous outcomes, we will produce boxplots and calculate the mean and corresponding confidence interval by allocated group for the measure at 28, 90 and 180 days and the change between baseline and 28, 90 and 180 days.

The simple, unadjusted estimated between-group difference of the change between baseline and 28, 90 and 180 days for each continuous outcome will be presented with the corresponding confidence intervals. The between-group differences, and corresponding 95% confidence intervals, adjusted for stratification variables will also be calculated using multivariable linear regression. The model will include both of the stratification variables (dichotomised baseline SADQ score and site).

For binary outcomes, we will produce calculations of the frequency and percentage (with corresponding exact 95% confidence interval) by allocated group. The unadjusted and adjusted between-group differences will be reported, derived from logistic regression models, with dichotomised baseline SADQ score and site included in the adjusted model.

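### The 180-day FIT–TAU difference in alcohol use makes no use of the 28- and 90-day readings of participants lost before day 180, and the protocol's check of lost against completing participants has no place in the SAP

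*SAP*

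**What the plan says.** Protocol 4.4 proposes change in grams of alcohol per week from baseline to 180 days as the definitive trial's primary outcome. Protocol 17.4 judges the promise of FIT on the confidence interval for the between-group difference in that change. Protocol 17.5 describes intention to treat as "including all the outcome data obtained from all participants". Protocol 17.4 also states: "Individuals lost to follow-up will be compared to those who complete the pilot study to identify any potential bias".

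The SAP puts this into practice as follows.

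- **Inclusion (4.2).** For change scores, "a participant will need to have non-missing or imputable data at both of the time points to be included in the analysis". Participants without a usable score "will not be included in the ITT analysis for the outcome/time-point under consideration".
- **Missed visits (4.7.1).** "Any participant who misses a follow-up visit or the whole outcome measure/questionnaire, will not be imputed for that time-point or measurement". Protocol 17.6 takes the same line: "As this is a pilot study, no imputation of missing data will be undertaken with the exception of instances where there are published methods".
- **Estimator (5.3).** "The simple, unadjusted estimated between-group difference of the change between baseline and 28, 90 and 180 days for each continuous outcome" is reported with confidence intervals. The adjusted version is a linear regression on site and dichotomised SADQ, with no earlier alcohol reading.
- **Table 11** is narrower still: change from baseline only in those who complete every follow-up visit.
- **Loss to follow-up (5.1.2)** covers reasons for withdrawal or loss. No section or table shell compares lost participants with completers.

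**The concern.** Someone who reports heavy drinking at days 28 and 90 and then cannot be reached contributes nothing to the 180-day contrast, although two readings that bear on their likely 180-day value are in the database. The estimate then describes those still reachable at day 180. As an estimate for everyone randomised, it is unbiased only if loss is unrelated to drinking, or if loss distorts both arms by the same amount so that the distortion cancels.

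Drinking-related loss is plausible here. Protocol section 1 reports that two-thirds of alcoholic hepatitis survivors relapse within six months, and section 10.6 makes follow-up depend on reaching people by telephone. The reasons for loss could also differ by arm, since FIT has nine scheduled nurse sessions and TAU one. At stake is the interval offered as evidence of promise. The comparison that would show whether this is a problem is promised in the protocol but absent from the SAP.

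**Working it through.** **1. The plan's own figure.** 90 recruited at 1:1 gives 45 per arm. 45 × 0.75 = 33.75, rounded down to 33, as in protocol 17.1 and SAP 3.5. Absent from the 180-day estimate: 90 × 0.25 = 22.5, so 22–23 people. At the edges of the amber retention band in SAP 5.5 the number is 36 (60% retained) or 18 (80%).

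**2. Where the bias comes from.** In each arm, the mean change among those retained differs from the mean change among all randomised by −p × G. Here p is the fraction lost, and G is the mean change of the lost minus that of the retained. The bias in the between-arm difference is one arm's shift minus the other's, so equal shifts cancel.

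**3. A case that can be checked by hand.** The documents give no SD or correlations, so these are assumptions:
- normal data in units of the SD of alcohol use at one visit;
- correlation 0.3 between baseline and each follow-up, and 0.5 or 0.7 between follow-ups;
- all loss after day 90, with log-odds of loss rising by 1 per SD of day-90 drinking.

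At 25% loss, the lost then drink about 0.85 SD more at day 90 than the retained (simulated). The shift in that arm's mean change is −p × (r between days 90 and 180 − r between day 90 and baseline) × 0.85:
- r = 0.5: −0.25 × (0.5 − 0.3) × 0.85 = −0.04 SD
- r = 0.7: −0.25 × (0.7 − 0.3) × 0.85 = −0.085 SD

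**4. Simulated bias in the between-arm difference.**

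| Assumed loss process | Bias (SD units) |
|---|---|
| Drinking-related, same in both arms, 25% each | about 0 |
| Drinking-related in one arm only, 25% each | 0.04 (r 0.5) to 0.08 (r 0.7) |
| Drinking-related in both arms, 35% v 15% lost | 0.03 to 0.07 |
| Drinking-related in TAU only, loss at every visit, r up to 0.8, log-odds 1–2 per SD | up to 0.50 − 0.38 = 0.12; mildest setting 0.50 − 0.48 = 0.02 |

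The sign depends on which arm has the drinking-related loss. If it is TAU, the FIT effect is understated; if FIT, it is overstated. Within an arm with such loss, change looks 0.04–0.08 SD too favourable at 25% loss, even when the difference between arms is unbiased. Using the day 28 and 90 readings brought the estimates in the first three rows to within about 0.003 SD of the full-data value, and gave 0.49–0.51 against a true 0.50 in the last.

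**5. Against the pilot's precision.** With baseline correlation 0.3, SD of change = √(2 × (1 − 0.3)) = 1.18. SE of the difference at 33 per arm = 1.18 × √(2/33) = 0.29. Half-widths are 1.15 × 0.29 ≈ 0.34 (75%) and 1.96 × 0.29 = 0.57 (95%). The largest bias is 0.12/0.29 = 0.41 of a standard error; 0.04 is 0.14 of one.

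**6. The SD for the definitive trial.** In the last row's scenarios, the 180-day SD among those retained is 1–9% too small. SAP 5.6 uses upper confidence bounds, which under normality multiply the SD by √((n − 1)/χ²): 1.13 (80% interval) and 1.17 (90%) at n = 66, and 1.20 and 1.26 at n = 33. Even the worst shortfall with the smallest multiplier gives 0.91 × 1.13 = 1.03 of the true value.

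**The case against.** The strongest reply is that this is a descriptive pilot and the plan does what it says. None of the four progression criteria in SAP 5.5 uses the effect estimate. SAP 4.3 and 5 rule out hypothesis tests and efficacy conclusions. Outcome visits are made by blinded researchers on one schedule in both arms, and the plan assumes non-differential retention. The possible bias is small beside the sampling error. All of this stands, and it limits the weight of the point.

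A reader might infer that the early readings of dropouts are thrown away, contrary to the protocol's intention-to-treat statement. The documents do not support that. Those readings enter the 28- and 90-day differences, the zero-consumption counts (Table 11b), the relapse counts (Table 13) and the Kaplan-Meier curves. Using each reading at its own visit is a tenable meaning of including all data obtained, and neither document promises a repeated-measures model.

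The simulations also favour the remedy by construction. Loss depends only on recorded values, so a model that uses those values must do well. They do not test loss driven by a relapse that was never recorded. Nor do they reflect intermittent gaps, which protocol 10.6 allows because contact resumes at the next visit. Loss before day 28 linked to high baseline drinking would pull the other way, because baseline is subtracted. Finally, grams per week may be skewed with many zeros, and a likelihood model implicitly predicts day-180 drinking for people who have died or been withdrawn for incapacity.

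What remains is that recorded data bearing on the key contrast go unused there, and that a comparison the protocol promises is missing.

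**Conclusion.** The point holds as a modest, inexpensive improvement. That no 28- or 90-day reading informs the 180-day contrast, and that the SAP contains no lost-versus-completed comparison, follows from the text alone. The size of any bias rests on assumed normal data, correlations and loss processes. It is about 0 under a common mechanism with equal retention, and about 0.04–0.12 SD if drinking drives loss in one arm only (0.02 in the mildest setting run). That is under half the standard error of 0.29 SD at 33 per arm. Within-arm change may look about 0.04–0.08 SD too favourable.

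Two further inferences should not be drawn. The documents do not show that dropouts had relapsed; the point concerns how such people would be handled, not how many there are. Nor is the SD in SAP 5.6 materially understated for planning, because the upper bounds used there exceed the simulated shortfall.

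**What to change.** - **Keep** the planned available-case difference as the simple description.
- **Add a supportive estimate.** Fit one repeated-measures model to alcohol use at 28, 90 and 180 days, with arm-by-visit, baseline-by-visit, site and SADQ-stratum terms and unstructured covariance. Include everyone with at least one post-baseline value. Report the 180-day contrast with 75%, 85% and 95% intervals, robust or bootstrap because of likely skew and zeros. State the missing-at-random assumption and report deaths separately.
- **Add a simple missing-not-at-random sensitivity analysis.** Shift the assumed 180-day mean of the lost by a range of amounts in each arm. The contrast moves by the fraction lost times the shift: at 25% lost, 0.1 SD in one arm moves it by 0.25 × 0.1 = 0.025 SD. This can be done on the arm means without imputing individual values.
- **Restore the protocol 17.4 comparison.** Put it in SAP 5.1.2 with a table shell: baseline characteristics and last recorded alcohol use, lost versus completed, by arm.
- **Label** these as post hoc if added after database lock. The SAP's revision note says that version 1.1 was itself made after lock with the statisticians unblinded.

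The cost is SAP wording, a few lines of code and one table, with no new data. The downside is one more model-based estimate to explain, which relies on missing at random and approximate normality.
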